In patients with resolved or chronic hepatitis B infection (inactive carrier state) or active controlled HBV infection on treatment with osimertinib:

- Recommend monthly monitoring of ALT/AST, HBV DNA levels and HBsAg (if negative at baseline)
- Where liver signs and symptoms of viral reactivation appear (HBV DNA levels exceeding 10-fold from baseline or ≥ 100 IU/ml (if baseline HBV DNA levels are undetectable) or conversion of HBsAg negative to positive):
 - Expert hepatologist/specialist oversight of the patient is required
 - Consider interruption or discontinuation of study treatment, based on risk-benefit assessment

I 3 Savolitinib dose modification and guidance

I 3.1 Savolitinib dose modification and guidance

Substantial acute toxicities should be managed as medically indicated and with temporary suspension of savolitinib, as appropriate unless due to suspected hypersensitivity (See section I 2.4).

Dose reductions or holds are allowed as clinically indicated by the treating physician and in line with [Table 22](#) and [Table 23](#). For each patient, a maximum of 2 dose reductions of

savolitinib will be allowed. No dose re-escalations are allowed. Guidance on dose level reduction is presented in [Table 22](#).

Table 22 Dose reduction for savolitinib to manage adverse events

Starting savolitinib dose	300 mg bid	300 mg od	600 mg od
Reduced dose -1	CCI	CCI	CCI
Reduced dose -2	CCI	CCI	CCI

Note: Only 2 dose reductions of savolitinib are permitted.

I 3.2 Dose modifications due to savolitinib-related toxicity

Dose modification guidelines for general savolitinib-related toxicities are shown in [Table 23](#) below. Appropriate and optimal treatment of the toxicity is assumed prior to considering dose modifications. Prior to discontinuation of savolitinib due to toxicities please consult with the study physician. Please see Section [I 3.3](#) for hepatotoxicity management guidelines and Section [I 3.4](#) for management of savolitinib specific toxicities including dermatologic toxicity, hypersensitivity, and QTc prolongation.

Table 23 Dose modifications for savolitinib-related toxicities

NCI CTCAE version 5.0 toxicity grade	Action
Grade 0, 1 or 2	None

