Grade 3 ^a 
 Grade 3 toxicity for ≤ 7 days. Grade 3 toxicity for >7 days. 	Hold dosing and follow algorithm below 
 Resume dosing at same dose or 1 reduced dose level (maximum of 2 dose reductions) as clinically appropriate^b Discontinue study drug
Grade 4 
 Expected to be manageable/reversible with dose reduction Not expected to be manageable/reversible with dose reduction 	
 Hold dose and consult with study medical monitor Discontinue study drug
Recurrence of Grade 3 
 Grade 3 toxicity for ≤ 7 days. Grade 3 toxicity for >7 days. 	
 Resume dosing at same dose or 1 reduced dose level (maximum of 2 dose reductions) as clinically appropriate^b Discontinue study drug
Recurrence of Grade 4	Discontinue study drug

^a Despite appropriate supportive care.

^b Restart of savolitinib must follow the specific restart guidelines if the event includes symptoms of pyrexia, skin reactions, myalgia, arthralgia, or hypersensitivity, as per section [I 3.4](#)

No more than 2 dose reductions of savolitinib will be allowed for any patient. Patients requiring additional dose modifications due to toxicity will discontinue savolitinib.

I 3.3 Hepatotoxicity management guideline

- Promptly evaluate patients with elevated LFTs during study treatment for alternative aetiologies and potential Hy's law criteria, and discontinue potential contributing concomitant medications or alternative causal agents, as well as anti-coagulants, if appropriate.
- If a patient discontinues due to LFT abnormality, LFT monitoring should continue until resolved to Grade 1 or baseline or an apparent plateau has been reached.

I 3.3.1 Dose modification due to drug-related hepatotoxicity

- Permanently discontinue drug if:
 - ALT or AST $>8 \times$ ULN with total bilirubin elevation above baseline or ULN, or
 - ALT or AST $>5 \times$ ULN for up to 1 week (<7 days) with total bilirubin elevation above baseline or ULN, following immediate withholding of savolitinib. Repeat LFT testing within 2 to 3 days and at least twice a week until improvement to Grade 1 or baseline.
 - ALT or AST $>3 \times$ ULN and (total bilirubin $>2 \times$ ULN or INR >1.5 if not on anticoagulants that elevate the INR), or

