Dermatologic: A case of Stevens-Johnson syndrome (SJS) has been reported in temporal association with savolitinib. Patients who show symptoms or signs suggesting emerging SJS while on study treatment (eg, progressive skin rash often with blisters or mucosal lesions), must discontinue savolitinib immediately and receive appropriate treatment. If emerging SJS is suspected, re-challenge with savolitinib must be avoided.

Hypersensitivity: Hypersensitivity, which may manifest as a constellation of symptoms such as but not limited to pyrexia, allergic skin reaction, increased liver enzymes, cytopenia, or myalgia and/or arthralgia has been reported after savolitinib dosing. These reactions have occurred within days to weeks after the first dose but the majority of reactions have occurred in the first six weeks of therapy. Patients with suspected savolitinib-related hypersensitivity (excluding confirmed infective aetiology), may be managed with corticosteroids, antihistamines and antipyretics (doses and duration of treatment according to local practice at the discretion of the investigator). Dose interruption with savolitinib should be avoided, if possible. Some patients who experienced the initial hypersensitivity reaction also reported severe acute hypersensitivity reactions, including anaphylaxis, upon restarting savolitinib treatment following a short period of interruption. If patients do need dose interruption, restarting savolitinib must be done under controlled conditions as per below. If the patient experiences an acute hypersensitivity or anaphylactic reaction, immediate intervention must be instituted and treatment with savolitinib should be permanently discontinued.

Restarting savolitinib: acute hypersensitivity including anaphylaxis has been observed in a number of patients mostly upon savolitinib restart. If interruption of savolitinib occurs in the first 6 weeks of study treatment due to savolitinib-related general toxicities, or specific

hypersensitivity toxicities occur at any time, dosing with savolitinib may be resumed but at a reduced dose, only after consultation with and approval from the study physician and with the following management:

- Treatment:
 - Pre-treatment with systemic corticosteroids must be started **at least** 24 hours before the restart of savolitinib;
 - Pre-treatment with antipyretics and antihistamines on the day of restart of savolitinib;

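### Table 23 footnote b omits the first-6-weeks restart trigger in Appendix I 3.4, so Table 23 read alone allows a same-dose savolitinib restart after an early, short Grade 3 general toxicity

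*Protocol*

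**What the plan says.** All of the texts are in the Protocol.

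- **Appendix I 3.1** makes Tables 22 and 23 the working reference for holds: "Dose reductions or holds are allowed as clinically indicated by the treating physician and in line with" those tables. Its pointer for suspected hypersensitivity is to section I 2.4, which does not exist; I 2 deals with hepatitis B reactivation.
- **Appendix I 3.2** divides the material: "Dose modification guidelines for general savolitinib-related toxicities are shown in" Table 23, while I 3.4 is cited "for management of savolitinib specific toxicities including dermatologic toxicity, hypersensitivity, and QTc prolongation".
- **Table 23**, in the rows for Grade 3 and for recurrence of Grade 3 lasting 7 days or less, says: "Resume dosing at same dose or 1 reduced dose level (maximum of 2 dose reductions) as clinically appropriate". Both cells carry footnote b: "Restart of savolitinib must follow the specific restart guidelines if the event includes symptoms of pyrexia, skin reactions, myalgia, arthralgia, or hypersensitivity", with a reference to I 3.4.
- **Appendix I 3.4**, in the paragraph on restarting, has two triggers. One is a time window: "If interruption of savolitinib occurs in the first 6 weeks of study treatment due to savolitinib-related general toxicities". The other is a specific hypersensitivity toxicity at any time. In either case "dosing with savolitinib may be resumed but at a reduced dose, only after consultation with and approval from the study physician". It then asks for corticosteroid, antipyretic and antihistamine pre-treatment, restart in the study hospital, vital-sign monitoring and 24 hours of observation. It closes by calling recommendations on hypersensitivity management and pre-treatment guidelines, and leaves final decisions to the investigator or treating physician.
- **Sections 7.1.1 and 8.4.5.2** refer the reader to Appendix I for restart. Neither mentions a 6-week window.

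**The concern.** Footnote b is where a site learns that Table 23 is not the whole story on restarting. It lists symptoms and no time window. I 3.2 has just told the reader that general toxicities belong to Table 23 and that I 3.4 is for specific ones. A site managing an early general toxicity with none of the listed symptoms could reasonably conclude that I 3.4 does not apply, and restart at full dose without approval, pre-treatment or observation.

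What is at stake is a safeguard the protocol already states. Section 2.3.1 names hypersensitivity, including anaphylaxis, as an important identified risk of savolitinib. I 3.4 reports that "acute hypersensitivity including anaphylaxis has been observed in a number of patients mostly upon savolitinib restart", and that most hypersensitivity reactions fell within the first six weeks, the window its restart rule covers. I 3.4 also lists cytopenia among the ways hypersensitivity may present. Footnote b does not list it, so an early isolated cytopenia not recognised as hypersensitivity would pass through Table 23. A time trigger does not depend on that recognition.

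**Working it through.** No sample size, power, error rate or estimate is involved, so the check is a comparison of triggers and permitted actions.

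**Triggers for the controlled restart**

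- Footnote b: pyrexia, skin reactions, myalgia, arthralgia, hypersensitivity. That is 5 symptom triggers and no time trigger.
- I 3.4: interruption for general toxicity in the first 6 weeks (6 × 7 = 42, so Days 1 to 42 if counted from first dose), or hypersensitivity toxicity at any time. That is one time trigger and one symptom trigger.

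Footnote b reflects only the second limb of I 3.4.

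**Four cases, each a Grade 3 general toxicity of 7 days or less**

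| Interruption | Footnote b symptom? | Table 23 with footnote b | I 3.4 | Agree? |
|---|---|---|---|---|
| Weeks 1–6 | No | Same dose or one level lower | Reduced dose, approval, pre-treated and observed restart | No |
| Weeks 1–6 | Yes | Sent to I 3.4 | Same rules apply | Yes |
| After week 6 | No | Same dose or one level lower | Not triggered | Yes |
| After week 6 | Yes (hypersensitivity) | Sent to I 3.4 | Same rules apply | Yes |

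The mismatch is confined to the first case. An example is isolated Grade 3 vomiting on Day 20 that resolves in 5 days. Liver enzyme rises and QTc prolongation fall outside it, because I 3.3 and Table 24 have their own rules.

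**Rows affected.** Two: Grade 3 for 7 days or less, and recurrence of Grade 3 for 7 days or less. The second is narrower, since it needs a second Grade 3 event within the window. The row for Grade 4 expected to be manageable asks for a hold and a consultation but states no restart dose, so it does not disagree with I 3.4.

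**Pointers elsewhere.** Of the two main-body sections that send the reader to Appendix I for restart (7.1.1 and 8.4.5.2), none names the 6-week trigger or says that I 3.4 limits Table 23.

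**The case against.** The strongest reply is that the two texts are layered. Section 8.4.5.2 allows repeat interruptions subject to further restart precautions in Appendix I, which suggests that I 3.4 sits on top of the dose-modification table. Table 23 leaves the choice of dose to clinical judgement, and I 3.4 narrows that choice early on. A site that picks the reduced dose and follows I 3.4 satisfies both. This stands: the rules can be reconciled. It does not close the gap, because the reader must already know that I 3.4 has a time trigger, and nothing outside I 3.4 says so.

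A second reply is that I 3.4 is itself partly advisory. This also stands in part. A reader might infer that I 3.4 flatly forbids any other restart, or might count its individual conditions against none in Table 23 as a measure of the gap. The documents do not support either reading, because the closing sentence makes pre-treatment and hypersensitivity management guidelines. That sentence does not clearly waive the reduced dose or the study physician's approval, and it does not put the time trigger into Table 23.

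A third reply concerns risk. A reader might infer that patients in the gap face a demonstrated risk of anaphylaxis on restart. The documents do not show this. The severe restart reactions that I 3.4 describes were in patients who had already had a hypersensitivity reaction, and footnote b already sends such patients to I 3.4.

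**Conclusion.** The point holds as a missing cross-reference with a safety consequence, and it is worth correcting. For a savolitinib-related Grade 3 general toxicity of 7 days or less, in the first 6 weeks, with no footnote b symptom and outside the liver and QTc rules, Table 23 with its footnote allows a same-dose restart. I 3.4 calls for a reduced dose, study physician approval and a pre-treated, observed in-hospital restart, with the pre-treatment element advisory.

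Its size is two rows of one table and one time window. The documents give neither the number of patients affected nor their residual risk, so the clinical effect cannot be quantified. No statistical quantity in the Protocol or SAP changes. The conclusion assumes that a site may work from Table 23 and footnote b without also reading the restart paragraph in I 3.4, which the wording of I 3.1 and I 3.2 makes plausible.

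**What to change.** Extend footnote b so that the I 3.4 restart rules apply if the event includes any of the five listed symptoms, or if the interruption occurs in the first 6 weeks of study treatment. The same-dose option in the two Grade 3 rows of 7 days or less then applies only after week 6 and without those symptoms. Leave I 3.4 and its closing sentence on guidelines unchanged; narrowing its trigger to match footnote b would remove a safeguard. In I 3.1, correct the cross-reference from I 2.4 to I 3.4.

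This needs one clause and one clerical correction, by amendment or clarification letter, and no new data. It helps only patients still in their first 6 weeks. The downside is that some early restarts will use one of the two permitted dose reductions and need the observed restart, with pre-treatment continued daily until savolitinib stops (steroids may be tapered). I 3.4 already asks for this.

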AESI Adverse event of special interest; CTCAE Common Terminology Criteria for Adverse Events; ECHO echocardiogram; ILD Interstitial lung disease; LVEF Left ventricular ejection fraction; MUGA multigated acquisition; SMQ Standardised MedDRA query; SOC standard of care.

The important identified risks for savolitinib are hepatotoxicity and hypersensitivity reactions (including anaphylaxis and Stevens-Johnson syndrome [SJS]). Specific monitoring and guidelines for toxicity management are in place to mitigate/manage these risks (see [Appendix I](#)).

Hepatotoxicity has been identified as a risk for patients receiving savolitinib and requires specific monitoring. Frequent monitoring of liver function tests will take place as outlined in the study plan. The hepatotoxicity management algorithm included in the protocol clearly defines and limits the patients who can be re-challenged to those with lower grade abnormalities with rapid resolution (see [Appendix I](#)). As stated in the eligibility criteria and risk mitigation sections, patients with abnormal baseline liver function tests will be excluded from the study and patients will be required to discontinue treatment with statins or reduce it to the lowest dose, prior to study entry.

CCI

followed in some cases by hepatotoxicity or an association of symptoms suggestive of hypersensitivity such as but not limited to allergic rash, cytopenias, myalgia/arthralgia and one case of SJS. Patients who experience hypersensitivity or pyrexia with or without an association of the above symptoms after initiation of savolitinib treatment must follow the toxicity management guidelines.

The QTc interval prolongation potential of savolitinib 600 mg was assessed in a thorough QT study in healthy volunteers. Analysis of the data concluded that it was a positive study, as the upper 2-sided 90% CI for the maximum mean Δ QTcF was 13.4 and 14 msec observed at 4 hours and 5 hours, respectively. Regular ECG assessments will be done throughout the study according to the study plan. Patients who present ECG abnormalities with or without symptoms during treatment with savolitinib must follow the QTc prolongation toxicity management guidelines (see [Appendix I](#)).

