 - AST or ALT $>3 \times$ ULN with the appearance of fatigue, nausea, vomiting, right upper quadrant pain or tenderness, fever, rash and/or eosinophilia $>5\%$
- Withhold dosing if ALT or AST $>5 \times$ ULN for > 2 weeks or $8 \times$ ULN without total bilirubin elevation above baseline or ULN, repeat LFT testing twice a week for 1 week:
 - If improved to Grade 1 or baseline in 1 week, resume at reduced dose with LFT testing twice a week for 6 weeks
 - If not, discontinue
- Withhold dosing if ALT or AST $>3 \times$ ULN and concurrent total bilirubin $>1.5 \times$ ULN, repeat LFT testing twice a week for 1 week:
 - If both ALT/AST and total bilirubin improved to Grade 1 or baseline in 1 week, resume at reduced dose with LFT testing twice a week for 6 weeks
 - If not, discontinue
- Withhold dosing if ALT or AST $>3 \times$ ULN and concurrent total bilirubin $>1 \times$ ULN to $1.5 \times$ ULN. Repeat LFT testing twice a week for 1 week:
 - If both ALT/AST and total bilirubin improve to normal range (< Grade 1) or baseline in 1 week, resume at same dose with LFT testing twice a week for 6 weeks
 - If not, resume at reduced dose, (as per bullet 3 above).
- Continue dosing if ALT or AST $>3 \times$ ULN without total bilirubin elevation above baseline or ULN, repeat LFT testing every week

- If ALT or AST trending upward, withhold dosing and repeat LFT twice a week for 1 week
- If improve to Grade 1 or baseline in 1 week, resume at same dose with LFT testing every week for 6 weeks
- If improve to Grade 1 or baseline in 2 weeks, resume at reduced dose with LFT testing every week for 6 weeks
- If not, discontinue
- Discontinue for recurrent ALT or AST $>5 \times$ ULN
- Discontinue for recurrent ALT or AST $>3 \times$ ULN and total bilirubin $>1.5 \times$ ULN
- Withhold dosing for recurrent ALT or AST $>3 \times$ ULN without total bilirubin elevation above baseline or ULN, repeat LFT testing twice a week for 1 week
 - If improve to Grade 1 or baseline in 1 week, resume at reduced dose with LFT testing every week for 6 weeks; if not, discontinue

I 3.4 Guidance for management of savolitinib specific toxicities

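### The savolitinib liver rules in Appendix I 3.3.1 give opposite instructions for the same findings, with no stated precedence for the permanent-stop criteria, and one branch literally allows restart without recovery

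*Protocol*

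**What the plan says.** Appendix I 3.3.1 opens with four criteria for permanent discontinuation, in multiples of ULN:

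1. ALT/AST >8 x, "with total bilirubin elevation above baseline or ULN, or" any of the others that follow.
2. ALT/AST >5 x for up to a week (under 7 days), "with total bilirubin elevation above baseline or ULN, following immediate withholding of savolitinib".
3. ALT/AST >3 x with either bilirubin >2 x or "INR >1.5 if not on anticoagulants that elevate the INR".
4. ALT/AST >3 x "with the appearance of fatigue, nausea, vomiting, right upper quadrant pain or tenderness, fever, rash and/or eosinophilia" above 5%.

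The later bullets relevant here are:

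- **Hold A** (third main bullet): ALT/AST >3 x with bilirubin >1.5 x. "If both ALT/AST and total bilirubin improved to Grade 1 or baseline in 1 week, resume at reduced dose"; otherwise discontinue.
- **Hold B** (fourth main bullet): ALT/AST >3 x with bilirubin >1 to 1.5 x. "If both ALT/AST and total bilirubin improve to normal range" or baseline within 1 week, resume at the same dose. Then: "If not, resume at reduced dose, (as per bullet 3 above").
- **Hold bullets for patients without raised bilirubin**: one for a first episode (>5 x for more than 2 weeks, or 8 x) and one for recurrent ALT/AST >3 x.
- **Continue dosing**: ALT/AST >3 x without raised bilirubin, with weekly tests.

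Section 2.3.1 says that the algorithm "clearly defines and limits the patients who can be re-challenged to those with lower grade abnormalities with rapid resolution". Appendix E 2 and SAP 3.2.2.3 define potential Hy's law as AST or ALT ≥3 x with bilirubin ≥2 x.

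**The concern.** Hold A has no upper limit on either value, and hold B has none on ALT/AST. Neither makes an exception for a patient who already meets a stop criterion. The bullets for patients without raised bilirubin exclude the bilirubin-based stops, but not the INR or symptom stops. A site could therefore follow a later bullet to the letter and re-expose a patient, or keep dosing one, whom the first bullet says to stop for good.

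Section 2.3.1 names hepatotoxicity as an important identified risk of savolitinib and relies on this algorithm to limit rechallenge. Where a stop collides with a hold, both instructions withhold drug at once and differ only on restart. Where a stop collides with the continue bullet, they differ immediately.

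**Working it through.** The plan gives no figure to reproduce. The check applies each rule to the same patient. Values are multiples of ULN.

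| ALT/AST | Bilirubin | Other finding | Stop criterion met | Later bullet also met |
|---|---|---|---|---|
| 4 | 2.5 | none | 3 | Hold A: restart at reduced dose |
| 9 | 1.8 | none | 1 | Hold A: restart at reduced dose |
| 9 | 1.2 (baseline normal) | none | 1 | Hold B: restart at same dose |
| 6 | 1.8, or 1.2 with normal baseline | none | 2, if it applies at detection | Hold A or hold B |
| 4 | 1.2 | INR >1.5 or a listed symptom | 3 or 4 | Hold B: restart at same dose |
| 9 | 0.8 | nausea | 4 | First-episode hold without raised bilirubin; also continue |
| 4 | 0.8 | nausea, or INR >1.5 | 4 or 3 | Continue dosing |

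The restarts shown apply to patients who recover within 1 week.

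**Extent of the bilirubin-based overlap.** Take a grid in steps of 0.1 x ULN, with ALT/AST up to 20 and bilirubin up to 6. Read raised bilirubin as >1 x ULN, and leave out INR and symptoms.

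- Pairs meeting hold A or B: ALT/AST 3.1 to 20.0 is 170 values and bilirubin 1.1 to 6.0 is 50 values, so 170 × 50 = 8,500.
- Pairs with no stop criterion: ALT/AST 3.1 to 5.0 (20 values) with bilirubin 1.1 to 2.0 (10 values), so 20 × 10 = 200.
- Pairs meeting both: 8,500 − 200 = 8,300.
- If criterion 2 is set aside, the stop-free block runs to ALT/AST 8.0: 50 × 10 = 500, leaving 8,000 in both.

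These counts describe rule coverage, not patients.

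**Dependence on baseline bilirubin.** Inclusion criterion 11 admits bilirubin up to 1.5 x ULN. The protocol does not say whether a rise above baseline or ULN means above either or above the higher. Under the higher-of-two reading with baseline 1.5, criteria 1 and 2 no longer overlap hold B. The overlap with hold A is unchanged, because that bullet starts above 1.5. The INR and symptom overlaps also stay.

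**Fallback branch of hold B.** The bullet it cites is hold A, which restarts at reduced dose only after recovery to Grade 1 or baseline within 1 week and otherwise discontinues. Hold B's fallback, read literally, restarts every patient who did not reach normal or baseline, including those with no improvement.

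**Potential Hy's law edge.** The stop uses >3 with >2; the definition uses ≥3 with ≥2.

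- ALT/AST >3 to 5 with bilirubin exactly 2.0 and no INR or symptom trigger: hold A only.
- ALT/AST exactly 3.0 with bilirubin ≥2: no bullet in I 3.3.1 applies.

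On the same grid, potential Hy's law covers 171 × 41 = 7,011 pairs, and the stop misses 20 + 41 = 61, all on the boundary.

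**The case against.** The strongest reply is that stop-first is the natural reading. The stop criteria come first, permanent discontinuation logically excludes resuming, and Section 2.3.1 states a restrictive intent. This is probably what was meant. It does not remove the conflict: the section uses explicit exclusions elsewhere (no raised bilirubin, or a bilirubin range), and holds A and B have none for patients who meet a stop.

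Safeguards also reduce the risk:

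- I 3.3 requires prompt evaluation against potential Hy's law.
- Appendix E 4.2 requires an SAE report within 1 day and study-physician contact.
- I 3.4 requires study-physician approval to restart after hypersensitivity toxicities, or after interruptions for general toxicities in the first 6 weeks.
- Section 6.6 leaves dose changes to the investigator, with sponsor discussion when needed, and I 3.2 asks for study-physician consultation before discontinuing for toxicity.
- Recurrence rules in I 3.3.1 mandate discontinuation for recurrent ALT/AST >5 x, or >3 x with bilirubin >1.5 x, so the conflict mainly concerns first episodes.

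These points stand as mitigation, but none says which instruction in I 3.3.1 applies. The version history mentions an Independent Hepatic Assessment Committee, but the committee text is redacted, so its role cannot be judged.

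Criterion 2 is also awkward: it can describe values that persist after a hold rather than a stop at first detection. On that reading the ALT 6 x examples fall away. The overlaps through criteria 1, 3 and 4 remain.

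Finally, hold B's cross-reference may be meant to import the Grade 1 condition from hold A. That is plausible, but the words do not say it.

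**Conclusion.** The point holds and should be fixed. The same findings carry opposite instructions in a safety rule, and precedence is unwritten. The fallback branch of hold B is a separate defect that reading order cannot cure. The ALT 9 x / bilirubin 1.2 x example assumes normal baseline bilirubin, and the ALT 6 x examples assume that criterion 2 applies at detection.

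Three stronger readings are not supported:

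- A reader might infer that the protocol intends to rechallenge Hy's law cases. Section 2.3.1 points the other way. The boundary mismatch concerns exact equality only, and Appendix E 1 disclaims being a full management guide, so its reporting limit need not equal a dosing limit. This part is minor.
- A reader might take 8,300 of 8,500 as a share of patients. It is not; the documents give no rates, so the number affected is unknown.
- A reader might infer that only the two bilirubin-elevated holds are involved. The INR and symptom stops reach the other hold bullets and the continue bullet too.

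The ORR analyses are unaffected.

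**What to change.** 1. State in I 3.3.1 that any permanent-discontinuation criterion, including the INR and symptom criteria, overrides every later hold, resume or continue bullet.
2. Reword the fallback branch of hold B. If values improve to Grade 1 but not to normal or baseline, resume at reduced dose; if they do not reach Grade 1 or baseline within 1 week, discontinue.
3. Set the stop limit at ALT/AST ≥3 x ULN with bilirubin ≥2 x ULN.

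Do not also cap the hold bullets at ALT/AST ≤5 x. The precedence sentence makes a cap unnecessary, and a cap could remove a needed hold. Take a patient with baseline bilirubin 1.4 x, now at ALT 6 x and bilirubin 1.2 x. If raised bilirubin means above the higher of baseline and ULN, no laboratory stop applies; hold B and the continue bullet both do. A 5 x cap would leave only the instruction to continue.

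The cost is a text-only protocol correction, with no change to visits, sample size or analysis. A few fast-recovering patients could no longer be rechallenged, which fits the intent stated in Section 2.3.1.
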